## **6 Insurance and Indemnity**

Clinical staff will be covered under the institutional Clinical Indemnity Scheme (CIS)

## **7 Reimbursement**

All participants will be reimbursed for travel and parking expenses incurred while

participating. Volunteers will not be paid to participate in this study.

## **8 Data management**

Data will be collected and stored in both paper and electronic format. Paper data will be filed and stored in a locked office at the Clinical Research Centre, St Vincents University Hospital. Electronic data will be password encrypted. All data will be handled in line with data protection legislation.

## **9 Statistical analysis**

Data will be analysed using GraphPad Prism (version 6.0) for Windows, GraphPad software (San Diego, CA, USA) and SPSS® (version 20.0) software (SPSS, Chicago, IL, USA). Central tendencies for patient and control group demographics, anthropometric data, caloric intake and macronutrient intake will be calculated and expressed using arithmetic mean  $\pm$  standard error of the mean or median (range), as appropriate. Differences in continuous variables between surgical and control groups will be calculated using the Student's *t* test or Mann-Whitney U test for parametric or non-parametric data, respectively. Correlative analyses will be performed using the Spearman Rho rank correlation to assess the relationship between *ad libitum* caloric intake and macronutrient intake with peri-operative weight loss and anthropometric data. Univariate analysis of factors associated with perioperative and post-surgical weight loss will be performed using Student's *t* test or one-way ANOVA for categorical variables or simple logistic regression for continuous variables. For the multivariate analysis, independent variables which were significant on univariate analysis, including standard demographic, food intake and food preference, will be entered into a multiple logistic regression model with a forward stepwise selection procedure to assess their impact on perioperative and post-surgical weight loss. All statistical analyses will be two-tailed with the threshold of significance set at  $P < 0.05$ .

Although the patients will be tested at all of the time points. Sample size has been estimated based on Gregersen *et al.*[2] who suggest that 35 patients will be required per group in an unpaired study design to detect a 300kJ difference in overall caloric consumption between two groups with a power of 0.8. We anticipate that single-sitting food intake after upper GI surgery will be approximately 60-80% that of matched controls. Given a control *ad libitum* caloric intake of approximately 600kcal, this would equate to a 120 – 240kcal difference in caloric intake. In addition, differences in preferred food types will be studied.

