## ***2 Study Objectives and Design***

### ***2.1 Objectives***

The primary objectives of this study are

[figure not shown]
1. Determine the effect of Roux-en-Y gastric bypass (RYGB) surgery on food preference using a standardised Buffet meal.
2. Determine if the changes in food preference following RYGB are mediated through changes in gut peptide following surgery.

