### ***2.2 Design***

The Study will be conducted in two parts. The first phase of the study is an observational component where participants who are due to undergo RYGB surgery in addition to a matched control group will have their food preference assessed using a standardised macronutrient self selection paradigm (MSSP). This process will be undertaken 1 months pre and 3, 12 and 24 months post surgical intervention (See figure 1). The control group will be studied at matched time points. This will allow determination of the primary outcome, whether RYGB surgery alters food preference. Phase two of the trial will focus on understanding potential mechanisms responsible for altered food preference. It will take the form of a randomised control study whereby subjects following RYGB and controls will be

invited to repeat the MSSP after randomly receiving octreotide or saline placebo in a blinded crossover fashion. This assessment will take place one year following surgery.

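### Section 9 gives the week -4 meal no role in the RYGB versus control comparison, although phase 1 is non-randomised and its controls are matched only on visit timing

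*Combined protocol and SAP*

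**What the plan says.** The first objective in section 2.1 is to "Determine the effect of Roux-en-Y gastric bypass (RYGB) surgery on food preference using a standardised Buffet meal". Section 2.2 describes phase 1 as observational, with a surgical group and a control group, and sets the meal schedule: "This process will be undertaken 1 months pre and 3, 12 and 24 months post surgical intervention". It says this design will answer the primary question, whether RYGB changes food preference. The section 4 visit list includes a buffet meal at week -4.

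In section 9, the whole provision for the group comparison is that "Differences in continuous variables between surgical and control groups" will be assessed by Student's t or Mann-Whitney. Nothing says whether the variable tested is a post-operative value, a change from week -4 or a baseline-adjusted value, and no visit is named. No paired, repeated-measures or group-by-time method appears; the one sentence about testing at all time points is incomplete. Group summaries are planned: "Central tendencies for patient and control group demographics, anthropometric data, caloric intake and macronutrient intake will be calculated".

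The sample-size text says that "35 patients will be required per group in an unpaired study design to detect a 300kJ difference" with power 0.8, and adds "We anticipate that single-sitting food intake after upper GI surgery will be approximately 60-80% that of matched controls", worked out as a 120-240 kcal difference. On preference it says only "In addition, differences in preferred food types will be studied".

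Controls are called matched in sections 2.2 and 9. Section 2.2 matches the time points of their visits. Section 3.1 describes them as healthy, free-living people without bariatric surgery and gives no matching variable, ratio or procedure.

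**The concern.** People listed for bariatric surgery and healthy volunteers may differ in what and how much they eat before any operation. With no randomisation and no stated matching on personal characteristics, the week -4 meal is the design's main protection against attributing such a difference to surgery, and the analysis section gives it no role in the test.

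If the t test is run on a post-operative visit alone, a lasting pre-existing gap is counted as a surgical effect, or a gap in the other direction hides part of a real one. Planned summaries may make a baseline gap visible, but the plan does not say how it would alter the conclusion. With the visit and the form of the outcome both open, the primary contrast could also be settled after the data are seen.

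**Working it through.** **Inputs from section 9.** 35 per group; difference 300 kJ; power 0.8; "All statistical analyses will be two-tailed with the threshold of significance set at" 0.05. The sample-size sentence itself states no alpha, so two-sided 0.05 is taken from the analysis paragraph.

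**Assumptions, not in the documents.** The SD (back-solved below), taken as equal in both groups and before and after surgery; the size and direction of any baseline gap; the pre/post correlation ρ. The documents give no SD or effect size for a preference measure, so all figures are for total energy intake.

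**1. The plan's own figure.** For a two-sample t test, the noncentrality is d × √(n/2), with d = difference/SD. With n = 35 (68 df, critical value 1.995), 80% power needs d = 0.679. Hence SD = 300/0.679 ≈ 442 kJ, or about 106 kcal at 4.184 kJ per kcal. The figure of 35 is consistent with this SD but cannot be reproduced independently, because no SD is stated. A one-sided 0.05 would imply d = 0.600 and SD ≈ 500 kJ.

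**2. Post-operative test only, no RYGB effect, lasting baseline gap.** The noncentrality is gap/SD × √17.5.

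| Gap (SD) | Gap (kcal) | Noncentrality | Rejection |
|---|---|---|---|
| 0.25 | 26 | 1.05 | 17.8% |
| 0.50 | 53 | 2.09 | 54.1% |

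For the same kcal gaps, SD 500 kJ gives 14.9% and 44.5%, and SD 600 kJ gives 11.8% and 33.0%.

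**3. Post-operative test only, surgical candidates eat more beforehand.** The effective d is fall/SD minus the gap.

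| True fall | No gap | 0.25 SD | 0.50 SD | 0.75 SD |
|---|---|---|---|---|
| 300 kJ (72 kcal) | 80% | 42% | 11% | 1% |
| 120 kcal | 99.7% | 96% | 75% | 36% |
| 180 kcal | >99.9% | >99.9% | 99.9% | 97.6% |
| 240 kcal | >99.9% | >99.9% | >99.9% | >99.9% |

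So masking matters at 300 kJ, which lies below the anticipated range, and towards the 120 kcal end. One gap cannot produce both step 2 and step 3.

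**4. Test on change.** The SD of change is SD × √(2(1−ρ)). A lasting gap cancels, so rejection under step 2 returns to about 5% (4.6-5.1% in simulation, 20,000 trials per scenario).

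| ρ | d for 300 kJ | Power, 35 per group | n per group for 80% |
|---|---|---|---|
| 0.3 | 0.679/1.183 = 0.574 | 66% | 49 |
| 0.5 | 0.679/1.000 = 0.679 | 80% | 35 |
| 0.6 | 0.679/0.894 = 0.760 | 88% | 29 |

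For 120 kcal, power is 97.7%, 99.7% and 99.9%. If the groups' courses would have diverged by 0.25 SD without surgery, the change test rejects 14%, 18% and 21%.

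**5. ANCOVA under a lasting gap.** In the same simulation, rejection at gaps of 0.25 and 0.5 SD was 11% and 31% at ρ = 0.3, and 8% and 17% at ρ = 0.6. It removes only part of a lasting gap.

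**The case against.** The strongest reply is that the plan never commits to a post-operative-only test. *Unpaired* means separate groups, and a t test on change between RYGB patients and controls is unpaired too. The sentence comparing intake after surgery with controls justifies the sample size and does not define the test. This stands. A reader might infer that the plan ignores baseline by design, but the documents support only that baseline use is unspecified. Steps 2 and 3 are therefore conditional.

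It is also fair that the figures concern energy intake while the primary question is food preference, and that the gaps and correlations have no anchor in the documents. This limits the arithmetic to illustration. It does not make the plan safer for preference, where section 9 offers no effect size, SD or power.

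Some design features narrow baseline differences. Section 3.1.2 excludes conditions and medications affecting food intake or preference, and section 3.5 aims to serve each subject foods given intermediate ratings. Neither removes confounding.

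Finally, placing change above ANCOVA is a judgement. Step 4 shows that a 0.25 SD divergence harms the change test about as much as a 0.25 SD lasting gap harms the post-operative test. That is why the assumption should be written down and ANCOVA reported beside it.

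**Conclusion.** The concern holds as a gap in the specification of the primary phase 1 comparison. Section 9 gives an unpaired test with no visit and no role for the week -4 meal, in a non-randomised comparison whose controls are matched only on timing. If the test is applied to post-operative values, a lasting gap of 0.25 or 0.5 SD gives about 18% or 54% rejection for energy intake with no RYGB effect. This rests on the back-solved 442 kJ SD, equal SDs and assumed gaps. Masking is small over most of the 120-240 kcal range.

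Two stronger inferences are not supported. The figures are not an error rate for this trial or for its preference outcome, since no gap is known and a test on change remains open. Nor do they show 35 per group to be wrong: that number fits its stated purpose under the implied SD. The missing matching variable is, on its own, only missing detail. It matters here because matching cannot stand in for baseline adjustment.

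**What to change.** In section 9, define the primary phase 1 comparison as the between-group difference in change from week -4 to one post-operative visit named before analysis. Choose a visit without an injection, since section 3.5 has eligible subjects injected before both 12-month meals; week 12 is one example. Use a mixed model with group, visit and group × visit, keeping week -4 as an outcome, or a t test on change. Apply it to the macronutrient preference outcomes as well as energy intake.

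State the assumption that the groups would have followed parallel courses without surgery. Note that the healthy-eating session given to everyone after the first visit (section 3.6) could affect the groups differently. Report a baseline-adjusted ANCOVA comparison as a sensitivity analysis.

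State that power for 300 kJ with 35 per group depends on the pre/post correlation: about 66%, 80% and 88% at 0.3, 0.5 and 0.6 under the assumed SD.

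Name the matching variables in section 3.1, or remove the word *matched* for the control group in sections 2.2 and 9. Reconcile the section 4 visit list, which has a buffet meal at week -4, with Table 2, which as extracted marks none at Visit 1. That may be a fault of PDF reading, but the fix relies on that meal.

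The cost is a rewritten paragraph, a power sentence and a matching statement, with no added visits or samples per participant. The downsides are lower precision than a single-visit test if the correlation is below 0.5 (at 0.3, 49 rather than 35 per group for 80% power at 300 kJ) and reliance on parallel courses.

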## **5 Adverse event program**

### **5.1 Subject premature Withdrawal**

If a study volunteer fails to complete the study protocol it will be documented in the individual case report form. The reason for failure to complete the study will be included in the CRF. Study Subjects may be withdrawn for the following reasons

- Adverse Event(s) (AEs)
- Abnormal laboratory value(s)
- Protocol violation
- Subject withdrew consent
- Lost to follow-up
- Death

All patients who withdraw early from the study will have their GP informed in writing that their participation in the study is complete. In the event of adverse event, GP's will be informed and arrangements will be made for subjects who have a requirement for ongoing medical follow-up as a consequence of an adverse event.

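### The only stated RYGB-versus-control test takes one value per person, so the 24 month contrast rests on people with a 24 month meal and is biased if attendance depends on earlier intake

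*Combined protocol and SAP*

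**What the plan says.** On timing, Section 2.2 says: "This process will be undertaken 1 months pre and 3, 12 and 24 months post surgical intervention". For controls it says: "The control group will be studied at matched time points".

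On the group comparison, Section 9 says "Differences in continuous variables between surgical and control groups will be calculated using" one of two methods: Student's t where the data are judged parametric, and Mann-Whitney where they are not. The other analyses there (Spearman correlation, ANOVA, logistic regression) concern correlates of weight loss. None compares the groups over time. The one sentence on the repeated visits breaks off: "Although the patients will be tested at all of the time points". The sample size that follows is that "35 patients will be required per group in an unpaired study design to detect a 300kJ difference", with power 0.8 and no allowance for dropout.

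On people who leave, Section 5.1 lists adverse events, protocol violation, withdrawn consent, loss to follow-up and death among the reasons. The only data rule is "If a study volunteer fails to complete the study protocol it will be documented in the individual case report form", with the reason recorded. Section 3.1.2 adds a post-operative exclusion for persistent surgical complications, which can apply only to the RYGB group. Section 3.2.2 provides that the data of anyone who withdraws consent are deleted.

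**The concern.** A two-sample test takes one value per person. With no imputation or longitudinal model stated, a test at 24 months can include only people who have a 24 month value. A change-from-baseline t test would have the same restriction. Someone who leaves after the 3 or 12 month meal still counts in the comparisons up to that point, but those meals do not inform the 24 month contrast, although intake at one visit predicts intake at the next.

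This matters if attendance is related to earlier intake. If RYGB participants who eat little stop coming, the remaining RYGB mean is too high and the group difference shrinks. If those who eat more stop coming, the difference is exaggerated. The visits concerned answer the first primary objective in Section 2.1.

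**Working it through.** **The plan's own figure.** Section 9 gives 35 per group, 300 kJ and power 0.8 at two-sided 0.05, but no SD, so the 35 cannot be reproduced independently. Solving backwards with the normal formula:

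SD = 300 / [(1.960 + 0.842) × √(2/35)] ≈ 448 kJ

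The noncentral t distribution gives 442 kJ, which is used below as an implied value. The low end of the anticipated difference in Section 9 is 120 kcal × 4.184 = 502 kJ.

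**Assumptions (the documents give none of these).** RYGB loss by 24 months is 20% or 30%. Controls are lost at random. The between-visit correlation ρ is 0.4 to 0.6. The log-odds of attending rise with 3 month intake by 0.5 or 1.5 per SD, so low eaters leave.

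**Bias of the attenders-only contrast.** Let z be standardised 3 month intake and k = E(z | still attending). The RYGB mean at 24 months, and so the difference, shifts by

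bias = ρ × SD × k

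Numerical integration over a normal z, with the intercept set to give the stated loss, yields:

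| Slope per SD | Loss | k | Bias, ρ = 0.4 | Bias, ρ = 0.6 |
|---|---|---|---|---|
| 0.5 | 20% | 0.096 | 17 kJ | 26 kJ |
| 0.5 | 30% | 0.143 | 25 kJ | 38 kJ |
| 1.5 | 20% | 0.227 | 40 kJ | 60 kJ |
| 1.5 | 30% | 0.327 | 58 kJ | 87 kJ |

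For example, 0.6 × 442 × 0.327 ≈ 87 kJ. Against 502 kJ the range is 3% (17/502) to 17% (87/502). Reversing the sign of the slope reverses the sign of the bias. A slope of zero gives k = 0 and no bias.

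**What using the earlier meal does.** In simulated trials of 35 per group (6,000 per scenario, controls lost at half the RYGB rate), an estimate that regresses the 24 month meal on the 3 month meal had bias within about 2 kJ in every row.

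**Precision.** In the same runs the standard error of the 24 month difference was 112-121 kJ for the two-sample contrast and 111-126 kJ for the regression estimate. The gain in precision is therefore negligible.

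**Data deleted on withdrawal of consent.** Suppose half of the dropouts have their data deleted. At loss d, the mean of z among people whose data remain is 0.5 × (1 − d) × k / (1 − 0.5d). For slope 1.5 this is 0.5 × 0.8 × 0.227 / 0.9 = 0.101 at 20% loss and 0.5 × 0.7 × 0.327 / 0.85 = 0.135 at 30%. Multiplied by ρ × 442, the residual bias is about 18-36 kJ, which no model removes.

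**Effect on power.** With 20% loss per group (28 left in each), power for 300 kJ falls from 0.80 to 0.70. For 502 kJ it is still about 0.95 at 40% loss.

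**The case against.** The strongest reply is that the harm is modest and rests on assumptions. The largest bias above, 87 kJ, is below one standard error at 30% loss: 442 × √(1/25 + 1/30) ≈ 120 kJ. Power for the remaining 415 kJ would still be about 0.93, and 502 kJ is the low end of what the plan anticipates. This stands. The point concerns the size of the 24 month estimate more than whether a large effect would be detected.

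Three stronger readings are tempting, and the documents do not support them.

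- A reader might infer that the plan prescribes a separate test at each visit on whoever attends and discards early data. Section 9 names a test and says nothing about visits or analysis sets. The restriction to attenders follows from the method, and it removes dropouts' meals from the later contrast only.
- A reader might infer that the 24 month effect is biased towards zero. That needs low eaters to leave, and nothing in the documents says who will leave.
- A reader might infer a large gain in precision, because averaging three visits multiplies the variance by (1 + 2ρ)/3, which is 0.60 at ρ = 0.4 and 0.73 at ρ = 0.6. That applies to a three-visit average, not to a visit-specific contrast such as the one at 24 months.

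**Conclusion.** The concern holds in this limited form. The stated test leaves the 24 month contrast open to selection, and a better method is available in software the plan already names. Under the assumed values the bias is about 17-38 kJ for weak selection and 40-87 kJ for strong selection. Its direction depends on who leaves, and it is nil under completely random loss.

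The SD is implied and not stated. The loss rate, correlation and slope are assumptions. The figures are for energy intake; the documents give no SD or effect for food preference, so the size there is unknown. The change should be made, but the trial's main conclusion does not stand or fall on it.

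**What to change.** Make the phase 1 primary analysis one linear mixed model for repeated measures, with group, visit, group-by-visit and an unstructured within-person covariance, fitted to all available phase 1 meals.

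- Include the baseline meal, as the first visit or as a covariate. Controls are not randomised, so report the RYGB-control difference in change from baseline at 3, 12 and 24 months with 95% confidence intervals.
- State that the week-52 saline meal, not the octreotide meal, supplies the 12 month value. Say also which meal is used for people excluded from octreotide.
- Keep the t or Mann-Whitney tests as supportive analyses.
- Report attrition and its reasons by group, and separately the number whose data were deleted.
- Add one sensitivity analysis that shifts the imputed values of RYGB dropouts over a stated range.

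The cost is SAP wording and a little programming in SPSS. No extra visits or participants are needed. Picking out the saline meal needs the treatment code, so the timing must be reconciled with the unblinding rule in Section 3.3. The model assumes data are missing at random, which the shift analysis probes, and it cannot recover data deleted under Section 3.2.2.

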### **Exclusion Criteria**

- Age <18 years
- Pre-operatively: Factors impairing ability to consume meal
  - Significant dysphagia
  - Gastric outlet obstruction
  - Anything factor that prevents subjects from eating a meal.
- Post-operatively: Factors impairing ability to consume meal
  - Significant and persistent surgical complications or
  - Anything that prevents subjects from eating a meal.
- Systemic or gastrointestinal condition which may affect food intake or preference
- Pregnancy or lactation
- Active and significant psychiatric illness including substance misuse
- Significant cognitive or communication issues
- Medications with documented effect on food intake or food preference
- History of significant food allergy and certain dietary restrictions
- History of liver disease or pancreatitis (Exclusion from Octreotide)
- History of bradyarrhythmia (Exclusion from Octreotide)
- Use of medications with potential serious interactions with Octreotide (Exclusion from Octreotide)

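### Surgical and control groups are compared with the equal-variance t test; if analysed sizes and spreads both differ, the standard error of the difference is wrong, and Welch's test corrects this at little cost

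*Combined protocol and SAP*

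**What the plan says.** Section 9 sets the method for surgical versus control comparisons: "Differences in continuous variables between surgical and control groups will be calculated using the Student's" t test for parametric data and the Mann-Whitney U test otherwise. It mentions neither unequal variances nor Welch's test. "All statistical analyses will be two-tailed with the threshold of significance set at" P < 0.05. Summaries are mean with standard error, or median with range; no confidence interval for the group difference is promised.

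On size, the same section relies on a cited reproducibility study: "35 patients will be required per group in an unpaired study design to detect a 300kJ difference in overall caloric consumption", with power 0.8. It expects that "single-sitting food intake after upper GI surgery will be approximately 60-80% that of matched controls", and from a control intake of about 600 kcal derives that "this would equate to a 120 – 240kcal difference in caloric intake". It states no SD for either group, no SD ratio, no allocation ratio and no dropout allowance.

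Section 2.2 describes phase 1 as observational, with a matched control group and visits up to 24 months after surgery. Section 3.1.2 lists a post-operative exclusion that only surgical participants can meet: "Significant and persistent surgical complications or" anything else that prevents eating a meal. Section 5.1 lists loss to follow-up among the withdrawal reasons.

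**The concern.** Student's t test uses one pooled variance. That is harmless when the groups are the same size or the spreads are the same. When both differ, the larger group dominates the pooled variance, and the standard error of the difference is too small or too large depending on which group is larger.

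Both conditions are plausible here. A group that eats less may also vary less. The groups are not formed by randomisation, are recruited by separate routes, and are followed for two years with no stated allowance for loss. This test carries the phase 1 group comparison, so its standard error decides how precise the intake difference appears.

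**Working it through.** **The plan's own figure.** For a two-sided 5% test with 80% power, n per group = 2 × (1.960 + 0.842)² × SD² / difference² = 15.70 × SD² / difference². Section 9 gives n = 35 and a difference of 300 kJ but no SD, so 35 can only be solved backwards: SD = 300 × √(35 / 15.70) = 448 kJ (442 kJ with the t distribution). That is consistent but circular, and gives no SD by group.

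**Inputs for the check.**
- From section 9: 35 per group, two-sided 5%, expected mean ratio 0.6-0.8.
- Assumed: SD ratio RYGB/control (r) of 0.6 or 0.8, which holds if SD scales with the mean; control SD set to 1; normal data; final sizes of 25 v 35 in either direction.

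**Formulas.**
- True SE² = r²/n₁ + 1/n₂ (n₁ RYGB, n₂ control).
- Pooled SE² ≈ [((n₁ − 1)r² + (n₂ − 1)) / (n₁ + n₂ − 2)] × (1/n₁ + 1/n₂).
- Non-coverage of a nominal 95% interval ≈ 2 × [1 − Φ(1.96 × pooled SE / true SE)].

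**35 v 35.** The pooled expression reduces to (r² + 1)/35, exactly the true SE². Simulation gives 5.0-5.1% for Student's and 5.0% for Welch at r = 1, 0.8 and 0.6.

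**RYGB 35 v control 25, r = 0.6.**
- True SE = √(0.36/35 + 1/25) = 0.2242.
- Pooled SE = √[(34 × 0.36 + 24)/58 × (1/35 + 1/25)] = 0.2070.
- Ratio 0.923: the standard error is about 8% too small. Non-coverage ≈ 7.0%.

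**RYGB 25 v control 35, r = 0.6.**
- True SE = √(0.36/25 + 1/35) = 0.2073.
- Pooled SE = √[(24 × 0.36 + 34)/58 × (1/25 + 1/35)] = 0.2245.
- Ratio 1.083: about 8% too large. Non-coverage ≈ 3.4%.

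The same steps at r = 0.8, with a simulation check (1,000,000 replicates per row):

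| RYGB v control | r | Pooled/true SE | Formula | Student's, simulated | Welch, simulated |
|---|---|---|---|---|---|
| 25 v 35 | 0.6 | 1.083 | 3.4% | 3.5% | 5.0% |
| 35 v 25 | 0.6 | 0.923 | 7.0% | 7.1% | 5.0% |
| 25 v 35 | 0.8 | 1.038 | 4.2% | 4.2% | 5.0% |
| 35 v 25 | 0.8 | 0.963 | 5.9% | 5.9% | 5.0% |

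**Is this type I error?** Not for total intake under the assumption used. The 60-80% is a ratio of means when surgery lowers intake. If SD scales with the mean, equal means imply equal SDs (r = 1), and Student's error is 5.0% at any split. The figures above therefore describe coverage of the true difference when means differ. They become false-positive rates only for an outcome with equal means but unequal spread. Macronutrient shares might be one, but the documents give no SDs for them.

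**Power cost of Welch.** With a difference of 300/442 = 0.68 control SD, Student's v Welch:
- 35 v 35: 80.0% v 80.0% (equal SDs); 92.4% v 92.3% (r = 0.6).
- 47 v 23, equal SDs: 75.0% v 74.2%.
- 50 v 20, equal SDs: 71.7% v 70.5%.

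With r = 0.6 and a difference of 0.6 control SD, Welch raises power from about 76% to 81% at 25 v 35, and lowers it from about 80% to 74% at 35 v 25. The fall largely reflects correction of a standard error that was too small.

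**The case against.** The strongest reply is that this is a general preference for Welch, not a defect peculiar to this plan. Three parts of that stand.

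First, the sample size is stated per group and the controls are called matched. At equal sizes the choice of test makes no material difference. A reader might infer that the plan leaves group size open; it does not. What it lacks is an allocation ratio and a dropout allowance, so equal analysed groups are intended but not assured.

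Second, a reader might infer from the 60-80% expectation that the test's 5% error rate really lies somewhere around 3-9%. The documents do not support that. The expectation concerns means when there is an effect, and under the scaling assumption the null hypothesis has equal SDs. The upper end also needs an SD ratio near 0.6 together with a split of about 1.8:1 or more in favour of RYGB (8.6% at 35 v 20), and neither is in the plan. The one asymmetry the plan names, exclusion for surgical complications, would shrink the RYGB group. If that group also has the smaller spread, Student's test is then conservative.

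Third, Welch is not entirely free, and its near-5% behaviour was shown for normal data. With strongly skewed intake (gamma-distributed, control coefficient of variation 0.8, SD ratio 0.6; all assumed), its error was 5.8% at 35 v 25 and 6.0% at 45 v 25, still better than Student's.

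A reader might also infer that the Mann-Whitney option must go. That is a separate and debatable change, and this point does not need it.

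What the reply does not answer is that an intake difference is estimated where means, and perhaps spreads, do differ. There the pooled standard error is wrong whenever the analysed sizes differ too.

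**Conclusion.** The point holds as a minor, cheap improvement. Its size is a standard error about 4% (SD ratio 0.8) to 8% (SD ratio 0.6) too large or too small at a 25 v 35 imbalance, moving non-coverage from 5% to roughly 3.5-7%. At 35 v 35 the effect is absent.

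This rests on assumed SD ratios, assumed final sizes and normal data. The documents give no SDs and do not show which group would end up smaller. For total intake the consequence is a misstated standard error and interval. A false-positive problem is possible only for outcomes with equal means and unequal spread.

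**What to change.** In section 9, replace Student's t test for surgical versus control comparisons with Welch's unequal-variance t test, and report the mean difference with its 95% confidence interval. The Mann-Whitney option can stay as written.

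The cost is one line of wording and no change to design or data collection. Power falls by at most about 0.1 point at 35 v 35, and by about 1 point at splits of 2:1 or more when SDs are equal. Larger falls occur only where the larger group has the smaller spread, the setting in which Student's test understates the standard error.
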